week baseline phase followed by a four-week intervention phase. The baseline intercept variable for this young person would be coded as 1, 1, 1, 0, 0, 0, 0, and the intervention intercept variable as 0, 0, 0, 1, 1, 1, 1. This coding will produce estimates of the mean baseline and intervention YP-CORE scores averaged across young people with individually varying phase lengths. Baseline and intervention intercepts can then be compared using a two-tailed Wald test to estimate a treatment effect; mean YP-CORE scores during the intervention phase are predicted to be significantly lower than mean YP-CORE scores during the baseline phase.

Two more dummy-coded variables will be included at level one to estimate the slopes for the baseline and intervention phases. The baseline slope variable will be coded for the weeks until the first intervention session, whilst the intervention slope variable will be coded for the weeks since the first intervention session. Continuing the example above of a young person with a three-week baseline phase and four-week intervention phase, the baseline slope variable would be coded as -3, -2, -1, 0, 0, 0, 0, and the intervention slope variable would be coded as 0, 0, 0, 0, 1, 2, 3. Note that the first intervention session is coded as a '0' across baseline and intervention time variables because it serves as the pre-treatment baseline (since the YP-CORE will be administered at the beginning of the first intervention session, before the intervention starts). This coding will produce estimates of the mean slopes during the baseline and intervention phases; a baseline slope not significantly different from zero, plus a significant negative intervention slope, would indicate a treatment effect. Furthermore, random intercepts and slopes will allow us to quantify stability and intraindividual variability in YP-CORE trajectories that would be observed in the visual analysis.

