Between-person covariates, including the randomly allocated start week, absolute time in weeks since the first participant was recruited, age, sex, ethnicity, free school-meal eligibility, and special education needs status, will be added to level two of the model to control for the confounding effects of method variables and demographics. We will also include interactions within time variables to investigate non-linear trajectories in YP-CORE scores, and interactions between time and demographic variables to investigate whether demographics moderate the treatment effect.

Multilevel models tend to be robust to deviations from their parametric assumptions (Maas & Hox, 2004). However, we will explore non-parametric alternatives, like Simulation Modelling Analysis (e.g., Dunn et al., 2019), if our data heavily violate these assumptions.

We will also estimate treatment effects and their effect size in line with standard outcomes reported in randomized controlled trials. For the treatment effect, we will use randomization tests, which, unlike more common tests of repeated measures like paired *t*-tests, do not make distributional assumptions or assume homogeneous variances (Bulté & Onghena, 2009). This is because the sampling distribution is based on random permutations of the observed data (i.e. a randomization distribution). We will also calculate a measure of effect size: Shadish et al.'s (2014) adapted *d*-statistic for single-case designs or Tau-U if there are trends in the baseline phase (Manolov, Losada, Chacón-Moscoso, & Sanduvete-Chaves, 2016).

Secondary Outcomes

Secondary outcomes include the RCADS, KIT Fidelity Checklist, and Implementation Survey. The RCADS will be completed at the start, middle and end of the intervention. We will use measures of central tendency and dispersion (e.g., means and standard deviations) to report group-level differences in scores between the baseline and intervention phases. Furthermore, we will evaluate the statistical significance of the difference in group means using parametric tests (e.g., repeated *t*-test), non-parametric (e.g., Wilcoxon Signed-rank test) tests, and regression models controlling for covariates, and quantify the size of the difference using the standardized mean difference (i.e. Cohen's *d*).

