We will also calculate Jacobson and Truax's (1991) clinically significant and reliable change indices for the RCADS. Clinically significant change tells us the proportion of young people who start the intervention in the clinical range and finish the intervention in the non-clinical or recovery range. There are different methods for calculating the thresholds for clinical and non-clinical/recovery ranges. We will use the RCADS' established clinical norms to determine the clinical range (e.g., *T* scores

> 69) and non-clinical range (e.g., T scores < 65; Chorpita, Moffitt, & Gray, 2005).

Reliable change refers to whether the changes observed in scale scores (both improvements and deteriorations) over the course of an intervention are greater than the change expected due to measurement error alone (Jacobson & Truax, 1991). We will calculate the proportion of young people who demonstrate reliable improvement, reliable deterioration, and no reliable change in the RCADS after receiving KIT. We will calculate reliable change indices from the sample data using Jacobson and Truax's (1991) formula for reliable change. We will also compare our findings to previous reports of reliable change indices for the RCADS (Edbrooke-Childs, Wolpert, Zamperoni, Napoleone, & Bear, 2018). Finally, we will determine the proportion of young people who showed both clinically significant and reliable change, since one can show reliable improvement without it being clinically significant, and vice versa.

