We will analyze all available outcomes on an intention-to-treat basis, including young people who did not start the intervention on the randomly allocated start week (e.g., due to school closures or pupil/practitioner absences) or complete the intervention. Missing data patterns will partly be caused by different baseline and intervention lengths; however, multilevel models can handle missing data due to varying treatment lengths (Ferron, Bell, Hess, Rendina-Gobioff, & Hibbard, 2009). We will assess whether clinical variables (e.g., baseline symptom scores), the randomly allocated start week, and demographic variables, predict dropout. Depending on proportion of missingness (e.g., >30% of observations) and its implied mechanisms, we will run a sensitivity analysis whilst handling missing data with methods such as multiple imputation.

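### The RCADS comparison is labelled as one between phases although the schedule supports only change from start to end of the intervention, and the paired tests given as examples would not use all available scores

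*SAP*

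**What the plan says.** All of this is in the SAP.

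- **Section {20a}, Secondary Outcomes, schedule:** "The RCADS will be completed at the start, middle and end of the intervention".
- **Same paragraph, contrast:** means and standard deviations will be used to "report group-level differences in scores between the baseline and intervention phases".
- **Same paragraph, tests:** a repeated t-test is the parametric example, followed by "non-parametric (e.g., Wilcoxon Signed-rank test) tests, and regression models controlling for covariates". Cohen's d is the effect size. The pair of occasions, the use of the middle score and the form of the regression are not stated.
- **Next paragraph, clinically significant change:** the proportion of "young people who start the intervention in the clinical range and finish the intervention in the non-clinical or recovery range".
- **Section {20a}, Primary Outcome, coding for the YP-CORE model:** in the worked example the first session belongs to the intervention intercept ("and the intervention intercept variable as 0, 0, 0, 1, 1, 1, 1"). In the slope coding the same session is zero on both time variables "because it serves as the pre-treatment baseline".
- **Section {20c}:** "We will analyze all available outcomes on an intention-to-treat basis". This expressly includes young people who do not complete the intervention. The section adds: "We will assess whether clinical variables (e.g., baseline symptom scores), the randomly allocated start week, and demographic variables, predict dropout". It also offers a conditional sensitivity analysis, with multiple imputation as an example and more than 30% of observations missing as an example trigger. Its remark that models cope with incomplete series concerns multilevel models and varying treatment lengths. The SAP names no multilevel model for the RCADS.

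**The concern.** In this trial, phase is a design term: the baseline phase is the run of weeks before a randomly allocated start, and the YP-CORE is collected weekly in it. The RCADS is not scheduled there. Calling its comparison one between phases suggests that it draws on the staggered baseline, when it is a pre-post change with no control. The label also does not say which scores enter the mean difference, the tests and Cohen's d.

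The second matter is what the example tests do with incomplete data. A paired t-test or Wilcoxon test run from start to end uses two of the three occasions and only those people who have both. Start and middle scores from someone without an end score would play no part, although {20c} says all available outcomes will be analysed. If those who drop out tend to be those who had improved less by the middle assessment, the remaining pairs overstate the improvement. A regression is also listed, but nothing says that it would use all three occasions.

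**Working it through.** The SAP gives no RCADS power, standard deviation, correlation or missingness rate, so there is no figure of the plan to reproduce.

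**1. Which contrast is meant.**

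| Reading of the start score | Baseline scores per person | Consequence |
|---|---|---|
| Intervention phase (as in the YP-CORE intercept coding) | 0 of 3 | No phase difference can be formed |
| Pre-treatment baseline (as in the YP-CORE slope coding) | 1 of 3 | Pre-post change can be formed; no baseline-phase mean or trend |

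Both codings were written for the YP-CORE and neither governs the RCADS. The paragraph on clinically significant change does concern the RCADS, and it compares start with finish. Start-to-end change is thus the sensible reading. It can be computed, but it is mislabelled, and the middle score has no stated role.

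**2. Precision of a paired analysis against a mixed model.** Input from the SAP: target N = 60 (Interim analyses {21b}). Assumed: unit SD, the same correlation r (0.6 to 0.8) between any two occasions, all start scores present, and 10% or 30% of end scores missing for reasons unrelated to the scores. That leaves n = 60 × 0.9 = 54 or 60 × 0.7 = 42 pairs.

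- Paired variance of the mean change: 2(1−r)/n.
- Mixed-model variance (large-sample): s/n + (2(1−r) − s)/60, where s is the residual variance of the end score given the earlier scores that were seen. With the middle score seen, s = 1 − 2r²/(1+r). With the middle score also missing, s = 1 − r².

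Example, r = 0.7, n = 42, middle seen: s = 1 − 0.98/1.7 = 0.4235. Paired variance = 0.6/42 = 0.014286. Mixed-model variance = 0.4235/42 + 0.1765/60 = 0.010084 + 0.002941 = 0.013025. SE ratio = √(0.014286/0.013025) = 1.047.

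Ratio of paired SE to mixed-model SE:

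| Pairs | Middle score | r = 0.6 | r = 0.7 | r = 0.8 |
|---|---|---|---|---|
| 54 | seen | 1.016 | 1.015 | 1.014 |
| 54 | also missing | 1.010 | 1.008 | 1.005 |
| 42 | seen | 1.050 | 1.047 | 1.044 |
| 42 | also missing | 1.031 | 1.023 | 1.015 |

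The paired SE is therefore 0.5% to 5.0% larger. Simulation at N = 60 with estimated regression coefficients (20,000 runs per cell, middle seen) gives slightly less: 1.015/1.014/1.014 at 54 pairs and 1.046/1.043/1.038 at 42 pairs.

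**3. Direction of bias if dropout follows poor early change.** Illustration only; every input except N = 60 is assumed. Means are 70, 67.5 and 65 (true change −5.0), SD is 10, and the log-odds of a missing end score rise by 0.15 for each point by which the start-to-middle change is worse. There were 3,000 runs per cell.

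| End scores missing | Start-end pairs, r = 0.5 | Start-end pairs, r = 0.7 | All three occasions |
|---|---|---|---|
| 10% | −5.6 | −5.4 | about −5.0 |
| 20% | −6.1 | −5.8 | about −5.0 |
| 30% | −6.6 | −6.1 | about −5.0 |

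The direction follows from the assumed dropout rule. The size depends on how strong that rule is made, and the SAP gives nothing to set it by.

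**The case against.** Much of the case on the other side stands.

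- **A reader might infer that the promised contrast cannot be estimated.** That takes the YP-CORE intercept coding as binding for the RCADS while discounting the slope coding, which treats the same session as pre-treatment. The start score is the natural baseline, and the clinical-change paragraph points the same way. The fault is one of labelling.
- **A reader might infer that the plan commits to dropping everyone without an end score.** It does not. Both paired tests are introduced as examples, start-end is never named as the tested pair, and a covariate regression is listed too. Leaving the intervention early need not mean having no end score, and a test on all available pairs may still include non-completers. What remains is conditional: if the paired tests are run start to end, they discard the middle score and incomplete pairs, and no RCADS analysis that would avoid this is specified.
- **A reader might infer that the ambiguity can halve the reported effect.** If the start score were compared with the mean of middle and end, the contrast would be (1+p)/2 of the start-to-end change, with p the share of change reached by the middle: 50% at p = 0, 75% at p = 0.5, 100% at p = 1. No section proposes that averaging, so this range is not a property of the plan.
- **Missing RCADS data are not ignored.** The dropout check and the sensitivity analysis in {20c} are not limited to the YP-CORE. The sensitivity analysis is conditional, however, and neither provision fixes the main RCADS analysis.
- **The RCADS text nowhere calls its difference a treatment effect.** That is so. The phase wording is what suggests a link to the randomised baseline, and correcting it removes the suggestion.

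**Conclusion.** The point holds as a wording error together with an analysis that could be better specified. The phase label does not match the RCADS schedule, the middle score has no stated role, and the paired tests fit poorly with the commitment to all available outcomes.

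The precision cost is small: about 0.5%-5% in SE, assuming 10%-30% of end scores missing, correlations of 0.6-0.8 and missingness unrelated to the scores. The stronger reason for change is protection from bias if dropout depends on earlier scores. The illustration shows which way that bias would run under one assumed rule, and its figures are not an estimate for this trial.

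Only a secondary outcome is concerned. The YP-CORE analysis is untouched. The change is worth making because it is cheap, not because the present plan would make the RCADS result unusable.

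**What to change.** In section {20a}, Secondary Outcomes:

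1. Replace the phase wording with RCADS change from start to end of the intervention, and describe it as an uncontrolled pre-post change.
2. Name one main analysis: a linear mixed model on all available start, middle and end scores, with time as a categorical factor and the planned covariates, reporting end minus start with its confidence interval. This gives the middle score a defined role.
3. State that the model assumes missingness at random given the observed scores and covariates.
4. Keep the paired t-test and Wilcoxon test as supportive analyses.

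The cost is a few sentences in the SAP and one model on scores already scheduled; no new data are needed. The drawback is the missing-at-random assumption, which the data cannot confirm, accepted for a small gain in precision and some protection from dropout bias.

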A Pragmatic Randomized Multiple Baseline Trial Evaluating Knowledge Insight Tools (KIT), a Cognitive Behavioural Therapy-informed School-based Counselling Intervention for Secondary School-aged Children and Young People with Anxiety and Mood Difficulties in the UK

Statistical Analysis Plans

NCT ID: Not yet assignment

Document Date: 01/08/2023

Statistical methods

Statistical methods for primary and secondary outcomes {20a}

Primary Outcome

The primary outcome is YP-CORE scores, assessed weekly throughout the baseline and intervention phases. We will analyze within-person and between-person change in YP-CORE scores using descriptive and inferential statistics suitable for multiple baseline designs.

Descriptive methods include summary statistics (e.g., measures of central tendency and dispersion) and visual analysis, where we will inspect time-series graphs of session-by-session scores for stability during the baseline phase, negative trends in the intervention phase, variability within and between phases, and the general degree of overlap between baseline and intervention scores using range lines (Lane & Gast, 2014).

Inferential methods include piecewise multilevel growth models to estimate within-person and between-person differences in average scores (i.e. levels) and the direction/rate of change in scores (i.e. slopes) between the baseline and intervention phases (e.g., Reut et al., 2023). Models will include at least two levels, with repeated observations of YP-CORE scores at level 1 nested within each young person at level 2. We will include additional levels if there is significant variation associated with specific therapists, schools, or regions. We will estimate fixed effects, which include intercepts and slopes averaged across young people for both the baseline and intervention phases (see below for piecewise coding of phases). We will also estimate random effects, which include between-person variation in intercepts and slopes for the baseline and intervention phases.

Two dummy-coded variables each representing an intercept for the baseline phase and intervention phase will be included in the model at level one. Each intercept variable will be coded to reflect the individually-varying break-points between baseline and intervention phases. Take, for instance, a young person with a three-

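### The missing-data sensitivity analysis is discretionary and names only multiple imputation, which in its usual form shares the primary model's assumption and is unlikely to reveal bias from outcome-related dropout

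*SAP*

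**What the plan says.** The primary analysis of weekly YP-CORE scores is set out in SAP section {20a}: "Inferential methods include piecewise multilevel growth models to estimate within-person and between-person differences in average scores". Two results can count as a treatment effect. One is a lower mean in the intervention phase than in the baseline phase, by a Wald test. The other is a flat baseline slope followed by a significantly negative intervention slope.

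Section {20c} deals with missing data:

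- The analysis set: "We will analyze all available outcomes on an intention-to-treat basis". This includes young people who do not complete the intervention.
- The source of missingness: "Missing data patterns will partly be caused by different baseline and intervention lengths". The word partly leaves room for other causes, but none is taken further.
- The defence of the model: "multilevel models can handle missing data due to varying treatment lengths". This covers unequal phase lengths. No assumption is stated for dropout.
- A check that is always run: "We will assess whether clinical variables (e.g., baseline symptom scores), the randomly allocated start week, and demographic variables, predict dropout".
- The condition for a sensitivity analysis: "Depending on proportion of missingness (e.g., >30% of observations) and its implied mechanisms".
- Its content: "we will run a sensitivity analysis whilst handling missing data with methods such as multiple imputation".

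The other sensitivity analyses, in sections {20a} and {20b}, concern fidelity and starting in the allocated week. They are not missing-data analyses.

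**The concern.** A sensitivity analysis should change the assumption in doubt. For dropout, that assumption is that, given the observed scores and covariates, leaving is unrelated to the scores that would have followed. A multilevel model fitted by likelihood to all available scores relies on it. So does multiple imputation in its usual form. If the imputation uses the same variables, the two analyses should agree whether or not the assumption is true, and their agreement could be mistaken for confirmation.

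The trigger adds to the problem. It is a matter of judgement, and its only figure is a proportion of observations. Bias depends on why young people leave as well as on how many leave.

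At stake is the main evidence of benefit. If those improving least leave early, the intervention slope looks steeper than it is. If those improving fastest stop early, it looks flatter.

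**Working it through.** The SAP gives no dropout rate, expected slope or variance, so there is no figure of its own to reproduce. The check has three parts.

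**1. What 30% of observations means.** Baseline weeks dilute the percentage. The participant used to illustrate the coding in {20a} has 3 baseline and 4 intervention scores. If every young person had that schedule and left halfway through the intervention, 2/7 = 29% of observations would be lost, which is under the example figure. With an assumed 4 + 9 scores, reaching 30% needs 0.30 × 13 = 3.9 lost scores per person. A halfway leaver loses 4.5, so 3.9/4.5 = 87% would have to leave halfway. Intermittent gaps are ignored here. The denominator is also unclear, because the SAP counts unequal phase lengths among the causes of missing-data patterns.

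**2. Does multiple imputation differ from the multilevel model?** Two simulations were run. All inputs are assumptions, and dropout is permanent.

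*Simulation A.* 4,000 young people per scenario; 4 + 9 scores; true intervention slope -0.5 points a week; SDs 6 (person), 0.6 (slope) and 4 (residual). The log odds of dropout rise by 0.7, 1.0 or 1.5 per SD of poorer slope. With 9% to 19% of observations missing, the multilevel model gave -0.57 to -0.79, and so did imputation from that model. At 17% missing the two gave -0.712 and -0.711. The overstatement runs from 0.07/0.5 = 14% to 0.29/0.5 = 58%, from rounded slopes.

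*Simulation B.* 6,000 young people; 3 + 8 scores; standardised units; true slope -0.10 a week; SDs 0.8, 0.10 and 0.6; the SAP's piecewise coding. The auxiliary variable is assumed to correlate about 0.8 with the true slope. Intervention slope per week:

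| Missing | Dropout | Complete data | Multilevel model | MI, same variables | MI + auxiliary | MI, imputed values +0.5 |
|---|---|---|---|---|---|---|
| 15% | at random | -0.1007 | -0.1016 | -0.1017 | -0.1026 | -0.0782 |
| 15% | driven by true slope | -0.0968 | -0.1269 | -0.1272 | -0.1108 | -0.1032 |
| 25% | at random | -0.0971 | -0.0985 | -0.0969 | -0.0964 | -0.0636 |
| 25% | driven by true slope | -0.1009 | -0.1500 | -0.1528 | -0.1250 | -0.1149 |
| 35% | at random | -0.0983 | -0.1035 | -0.1080 | -0.1065 | -0.0625 |
| 35% | driven by true slope | -0.0975 | -0.1681 | -0.1746 | -0.1404 | -0.1245 |

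- The largest gap between the multilevel model and same-variable imputation in the table is 0.1746 - 0.1681 = 0.0065.
- Overstatement by the multilevel model when the true slope drives dropout: 0.1269/0.0968 = 1.31, 0.1500/0.1009 = 1.49 and 0.1681/0.0975 = 1.72.
- The auxiliary variable removes part of the bias. At 15% missing, relative to the multilevel model, this is (0.1269 - 0.1108)/(0.1269 - 0.0968) = 53%. At 35% it is (0.1681 - 0.1404)/(0.1681 - 0.0975) = 39%.
- The shift moves the estimate in every row, including those missing at random, where it moves it away from the complete-data value. It is a probe of the assumption and does not correct the estimate.

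**3. At the target of 60 participants** (simulation B, 60 replicates each):

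| Missing | Dropout | Mean MI minus multilevel | SD of that difference | Slope SE |
|---|---|---|---|---|
| 15% | at random | -0.0001 | 0.0092 | 0.0199 |
| 15% | driven by true slope | -0.0011 | 0.0060 | 0.0188 |
| 25% | at random | +0.0009 | 0.0194 | 0.0227 |
| 25% | driven by true slope | -0.0030 | 0.0118 | 0.0209 |

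When the true slope drives dropout, the bias is (0.1294 - 0.0987)/0.0188 = 1.6 standard errors at 15% missing and (0.1483 - 0.0975)/0.0209 = 2.4 at 25%. No result is available at 35% and N = 60, because the fitting failed numerically.

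For simulation A, a rough complete-data standard error at N = 60 is √[(0.6² + 4²/60)/60] = 0.10. The first 60 is the sum of squared week deviations over 9 weekly scores. The bias there is 0.07/0.10 = 0.7 to 0.29/0.10 = 2.9 standard errors.

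**The case against.** The strongest reply is that the plan is more open than the concern suggests. Four parts of it deserve an answer.

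- *The trigger.* A reader might infer that the check runs only above 30% missing. The SAP does not say so: 30% is an example, and the apparent mechanism is a second consideration. This stands. The weakness is a discretionary trigger with an unhelpful example. It is not a fixed gate.
- *The method.* A reader might infer that imputation must return the primary answer and cannot expose bias. That also goes too far. The wording allows other methods, and imputation with auxiliary variables or a delta adjustment would differ. Even same-variable imputation differs within a single trial. But the plan commits to none of these alternatives, and the usual form of the one named method keeps the same assumption.
- *The existing checks.* The analysis of dropout predictors is always run, and complete and incomplete KIT interventions are compared. Neither addresses unobserved outcomes after dropout. The listed predictors are baseline symptoms, start week and demographics, and none is response during the intervention. Several are already in the primary model: "Between-person covariates, including the randomly allocated start week, absolute time in weeks since the first participant was recruited, age, sex, ethnicity". No analysis of observed predictors can rule out dropout that depends on unobserved scores.
- *The simulations.* Both biased cases assume that poor response drives dropout, which builds in the bias reported. By symmetry, early stopping by fast improvers would understate the slope by similar amounts. Only the slope was examined; the phase-mean contrast and the randomization tests were not. This stands and limits what the percentages can show.

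**Conclusion.** The point holds in a limited form. The SAP leaves the missing-data sensitivity analysis to judgement and names one method. In its usual form and on the same variables, that method makes the same missing-at-random assumption as the primary model and gives essentially the same estimate. No analysis under a different assumption is committed to. As specified, the plan is unlikely to reveal bias from outcome-related dropout, and agreement between the two analyses could reassure falsely.

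The close agreement appeared in both simulations despite different inputs. It presumes that the multilevel model is fitted by likelihood, which the SAP does not state. The bias figures, 14% to 58% at 9% to 19% missing and about 30% to 50% at 15% to 25% missing, rest wholly on assumed inputs. They show that bias can matter below the example threshold. They should not be read as a forecast that this trial will overstate benefit, because the SAP does not allow the size or direction to be known.

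**What to change.** Replace the conditional sentence in {20c} with a commitment along these lines:

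1. State the missing-at-random assumption of the primary model for dropout.
2. Whatever the percentage missing, run a delta-adjusted (pattern-mixture) imputation of YP-CORE scores after unplanned dropout. Keep planned or agreed endings separate, so that a short but finished intervention is not treated as missing.
3. Fix the grid of shifts in advance, in both directions, for example up to 0.5 points per missed week. On simulation A's assumed slope, +0.5 a week would cancel the whole improvement after leaving. The investigators should justify their own range.
4. Apply it to both the phase-mean contrast and the intervention slope, and report the shift at which each conclusion changes.
5. Keep missing-at-random imputation only if it adds auxiliary variables, such as RCADS or fidelity scores. These may themselves be missing after dropout, so they supplement step 2 and do not replace it.

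The cost is modest extra programming and a definition of each person's intended end of intervention, which the number of missed weeks depends on. No new outcome data are needed.
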